#### PROTOCOL HISTORY

Version Date (dd-mmm-yyyy)	Description
24 Sep 2015	Initial Release
12 Apr 2016	Initial IRB Approval
25 May 2016	Amendment 1
15 Jul 2016	Amendment 2
10 Jan 2017	Annual Renewal + Amendment 3
15 Mar 2017	Amendment 4
24 May 2017	Amendment 5
26 Jul 2017	Amendment 6
05 Dec 2018	Amendment 7 – add 6 subjects
05 Nov 2021	Amendment 8 – change to BioCue™ device

**SYNOPSIS**

Title of Study	Safety and efficacy of concentrated autologous concentrated bone marrow aspirate (BMAC) in preventing wound complications in amputations
Objectives	

• Determine the safety and explore efficacy of BMAC in preventing wound complications in amputations.

• Characterize the host tissue response to, paracrine activity of, and fate of transplanted BMAC.

• Determine the effects of chronic limb ischemia and diabetes on nerve function and to assess the effects of mesenchymal stem cell administration on their function.

Planned Number of Subjects and Duration of Involvement	12 patients, 12 month follow up period
Patient Population	Critical limb ischemia (CLI) patients scheduled for amputation
Investigational Product Name	Concentrated autologous bone marrow aspirate (BMAC)
Methodology Overview	
This is an open label pilot trial.
 
Up to twelve (12) patients scheduled for amputation will receive bone marrow cells concentrated (BMAC) via the BioCue™ Platelet Concentration Kit device injected IM at 25 sites in the leg proximal to the amputation in the index limb to prevent ischemic wound complications after surgery. BMAC will be injected into the anterior tibialis muscle (ATM) below the point of amputation for analytical purposes. Patients will be scheduled for amputation at Day 7 post injection. Safety will be evaluated by review of treatment related adverse events (AE) during the 12-month follow-up period. In subjects undergoing BKA, we will compare rates of wound complications and conversion from BKA to AKA to historical controls at our institution to assess trends in therapeutic efficacy.
 
Patients will undergo amputation and injection sites will be harvested from the ATM at that time. Immunohistochemical staining (IHC) will determine capillary density and local host immune responses. Angiogenic and inflammatory cytokines will be quantified using a multiplex array system and quantitative polymerase chain reaction (PCR).

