**Table 3. Inclusion/Exclusion Criteria for Enrollment of Subjects**

Inclusion criteria	

1. Be <math>\geq 40</math> and <math>\leq 90</math> years of age.

2. Patients requiring lower extremity major amputation, as determined by an independent vascular specialist.

3. If ulceration or gangrene is present, it is distal to malleoli (to allow adequate length of ATM area of approximately 3 cm x 10 cm x 3 cm)

4. Amputation can safely be performed up to 30 days after screening, as determined by an independent vascular or orthopedic surgeon.

5. Females of childbearing potential must be willing to use one form of birth control for the duration of the study. Female participants must undergo a blood or urine pregnancy test at screening.

Exclusion criteria	

1. Patients who are pregnant, planning to become pregnant in the next 12 months, or lactating.

2. CHF hospitalization within the last 1 month prior to enrollment.*

3. Acute coronary syndrome (ACS) in the last 1 month prior to enrollment.*

4. HIV positive or active, untreated HCV as determined by review of medical records.

5. History of cancer within the last 5 years, except basal cell skin carcinoma.

6. Inability to provide written informed consent due to cognitive or language barriers (interpreter permitted).

7. Concurrent enrollment in another clinical investigative trial.

8. Any condition requiring immunosuppressant medications (e.g., for treatment of organ transplants, psoriasis, Crohn's disease, alopecia areata).

9. Presence of any clinical condition that in the opinion of the PI or the sponsor makes the patient not suitable to participate in the trial.

\*As defined by the standard definitions of CHF and ACS by the American Heart Association.

Participant Withdrawal Criteria	At the discretion of the investigator or at the request of the participant.
--	---

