#### **6.1.2 Safety issues**

Safety of the BioCue™ device to concentrate BMA for the prevention of wound complications in amputation will be determined by review of treatment related adverse events (AE) and serious adverse events (SAE) during the study period of 12 months by the Data Safety Monitoring Board (DMSB) appointed by the Clinical and Translational Sciences Institute (CTSI) at the Indiana School of Medicine or Data Safety Committee (DMC) designated by the Principal Investigator.

The BMAC dose proposed in this trial was selected based on prior clinical trials. We may not see any evidence of efficacy in our composite endpoint, which may reflect an inadequate dose or sample size. In this case we would propose a future study exploring escalating doses of BMAC. In the instance of evolving infection, we would re-assess our inclusion/exclusion criteria and evaluate the contribution of pre-amputation procedures on the lower leg. Patients may request earlier amputation due to worsening rest pain or anxiety. Consideration for amputation sooner than one week post injections will be determined by the PI based on the severity of the subject's condition, so as to offer this research as an option to all eligible subjects.

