## **7** STUDY PROCEDURES

### **7.1** Workflow

[figure not shown]
The necessity for amputation will be determined by a vascular or orthopedic surgeon not participating in the study. After that decision has been rendered, the patient will be screened for enrollment. After enrollment, 12 patients requiring major amputation for CLI will be scheduled for amputation approximately one week post-BMAC injection in the ATM. Autologous BMA will be retrieved per standard institution procedures. The BioCue™ device will be used per manufacturer instructions.

Patients will receive IM injections of BMAC into the ATM below the point of amputation and up to 25 mL

[figure not shown]
of BMAC in the proximal leg above the point of amputation. Delivery of up to 25 sites of up to 1 mL each of BMAC will be performed in 2 cm increments along the lateral and medial aspects of the upper leg and gastrocnemius to ensure an even distribution. Patients will then undergo amputation approximately one week after injections. Patients will be examined at Baseline, BMAC Injection Day, Day of Amputation, Day 3 post-op amputation, and Weeks 2, 6, 12, 18, and 24 after amputation. At any time during a subject's participation, photographs of current wounds (as applicable at baseline visit) and photographs of the subject's amputation site (at follow-up visits) may be taken to assess wound healing. There will be a week 52 phone call to assess the patient for primary endpoints. Incidence of wound infection, minor (debridement of skin), and major revision (debridement of muscle and bone) of the amputation stump, and revision of amputation will be recorded. Rates of revision of amputation at 12 months will be compared to historical controls. The initiation of treatment will be staggered by a minimum of one week for the first 3 subjects to ensure that potential study treatment-related risks to subjects are minimized.

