**Determine the safety and explore efficacy of BMAC in preventing wound complications in amputations.** In a Phase I trial, BMAC (up to 3 mL) will be injected into the ATM below the point of amputation in the index limb. At the same time BMAC (1 mL) will be injected at up to 25 sites in the proximal leg to promote tissue perfusion before amputation (**Figure 3, Figure 4**). Patients will be scheduled for amputation approximately one week post-injections. Safety will be evaluated by review of treatment related AEs during the 12-month follow-up period. Efficacy will be assessed by rates of wound complications and revision of amputation to historical controls at our institution to assess trends in therapeutic efficacy.

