#### **BMAC Administration: Anterior Tibialis Muscle.**

On the day of BMAC injection in the operating room of the Richard L. Roudebush VA Medical Center, the index limb will be marked for amputation. The injection site area is marked on the anterior compartment of the lower leg below the point of amputation. The BioCue™ product is injected along a 3 cm tract into the anterior tibialis muscle (ATM). The injection site(s) will be marked with permanent ink on the ATM. The BMAC suspension will be injected over 3 minutes with the needle retracted 5 mm simultaneously to permit infiltration into the muscle.

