**Table 4. Schedule of Events**

Procedures	Baseline Visit 1	BMAC Injection Visit 2	Amp Day Visit 3	Day 3 F/U + 5 days Visit 4	Week 2 F/U +/- 2 days Visit 5	Week 6 F/U +/- 4 days Visit 6	Week 12 F/U +/- 7 days Visit 7	Week 18 F/U +/- 2 weeks Visit 8	Week 24 F/U +/- 2 weeks Visit 9	Week 52 Phone Call
Informed Consent	X									
Medical History	X									
Physical Exam	X	X	X	X	X	X	X	X	X	
Vital Signs	X	X	X	X	X	X	X	X	X	
Con. Medications	X	X	X	X	X	X	X	X	X	
AE/SAE Evaluations		X	X	X	X	X	X	X	X	
Laboratory evaluations	X 				X 	X 	X 	X 	X 	
12 Lead ECG	X				X		X		X	
LEADs / TcPO2	X 				X 	X 	X 	X 	X 	
Photograph of index leg / amputation site	X 				X 	X 	X 	X 	X 	
Schedule Amputation	X									
Research Blood Specimen 		X	X		X	X	X	X	X	
Evaluate for infection, gangrene				X	X	X	X	X	X	X
Evaluate necessity for amputation revision				X	X	X	X	X	X	X
Screening Laboratory Tests: CBC w/diff/plt; CMP (Sodium, Potassium, Chloride, CO2, Glucose, Calcium, BUN, Creatinine); eGFR, hsCRP										
Baseline only: Serum pregnancy testing (childbearing females)										
Follow-up labs: hsCRP										
TcPO2: Transcutaneous Oxygen Pressure; LEADs or Foot TcPO2  will be collected as a baseline measurement, TcPO2 of medial and lateral stump site  will be collected at follow up visits										
Photographs: Index leg at baseline  , BKA stump site at follow up visits  . It is not considered a protocol deviation if photographs were not performed.										
Research blood specimens: Collected prior to induction of surgery (BMAC Injection Day, and Amputation Day) from peripheral vein of up to 30 mL, and at follow-up visits at weeks 2 through week 24. It is not considered a protocol deviation if research blood collection is not performed.										

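### The Synopsis limits the BKA comparison to subjects who actually undergo BKA, and no section says how events between injection and amputation are counted

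*Combined protocol and SAP*

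**What the plan says.** The Synopsis sets the timing, "Patients will be scheduled for amputation at Day 7 post injection", and section 7.1 repeats it less strictly: "scheduled for amputation approximately one week post-BMAC injection in the ATM". Under Table 3, subjects must be able to wait: "Amputation can safely be performed up to 30 days after screening".

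The planned level is known before treatment. On injection day "the index limb will be marked for amputation", and the tibialis injection area is placed below the point of amputation (section 7.1). The legend to Figure 4 refers to the anticipated point.

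The efficacy population is described in two ways:
- Synopsis: "In subjects undergoing BKA, we will compare rates of wound complications and conversion from BKA to AKA", with historical controls at the institution as comparator.
- Sections 3 and 7.1, without a BKA restriction: "Efficacy will be assessed by rates of wound complications and revision of amputation to historical controls at our institution". Section 9.3 adds a 6-month composite of death, revision of amputation and gangrene, also unrestricted, and gives neither a time origin nor a denominator.

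Follow-up visits in section 7.1 are timed from amputation. In Table 4 the row "Evaluate for infection, gangrene" is first marked at Visit 4 (Day 3 after surgery), as is the row on need for revision. Physical examination and AE/SAE evaluation are marked at Visits 2 and 3. Section 6.1.2 allows for trouble before surgery, "Patients may request earlier amputation due to worsening rest pain or anxiety", and leaves earlier amputation to the PI, but attaches no endpoint rule.

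**The concern.** What the trial gives a patient is an injection followed by a wait of about a week, and then an amputation. A comparison group formed from the amputation performed is formed after treatment has begun. If ischemia or infection advances in that week and the first amputation is done above the knee, the patient has lost the joint that the Introduction gives as the reason for preferring BKA. Under the Synopsis that patient is no longer in the comparison. Under the other sections the patient remains but has had neither a conversion nor a revision.

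Section 9.3 plans to reject a null hypothesis of no change against historical cohorts, and section 3 says the results will frame a randomized Phase II trial. With at most 12 subjects, one or two such cases would shift the trend carried into that design.

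**Working it through.** The plan has no figure to reproduce: section 9.1 claims no power for efficacy, and 12 is a cap. The check is first a reading of the sections, then an illustration of scale.

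**Step 1. Follow three subjects, each planned for BKA on injection day.**

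| Course | Synopsis | Sections 3 and 7.1 | Section 9.3 composite |
|---|---|---|---|
| BKA performed, later converted to AKA | counted, event | event (revision) | event (revision) |
| First amputation is an AKA, stump heals | outside the denominator | no event | no event |
| Dies before amputation | outside the denominator | no rule | death is a component, but with no time origin or denominator its status is open |

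The second row goes unrecorded as a failure under every section. The third depends on choices the plan does not state.

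**Step 2. Check the schedule.** Need for revision cannot be judged before an amputation, so starting that row at Visit 4 is unavoidable. The infection and gangrene row could start earlier, because Visit 3 already has a physical examination. No listed procedure records the level planned against the level performed.

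**Step 3. Check whether safety data close the gap.** AE/SAE evaluation starts on injection day. However, section 9.3 analyzes treatment-related events, and section 10.1 does not collect or analyze AEs unless the investigator judges them serious and research related. Progression attributed to the underlying disease could go uncounted there too.

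**Step 4. Illustrate the scale.** Inputs:
- n = 12, the cap in section 4.1, all assumed planned for BKA.
- x = 2 later conversions (assumed). The Introduction's upper figure of 19% would give 12 × 0.19 = 2.28.
- k = number of index AKAs after the wait (assumed, since the documents give no rate), each with a stump that then heals.

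The three rules are: Synopsis x/(12 − k); unrestricted sections x/12; all injected by planned level, with an index AKA as an event, (x + k)/12. The 95% Wilson intervals borrow the method that section 9.3 names for AEs.

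| k | Synopsis | Unrestricted sections | All injected, by planned level |
|---|---|---|---|
| 0 | 2/12 = 16.7% | 2/12 = 16.7% | 2/12 = 16.7% |
| 1 | 2/11 = 18.2% (5.1 to 47.7) | 2/12 = 16.7% (4.7 to 44.8) | 3/12 = 25.0% (8.9 to 53.2) |
| 2 | 2/10 = 20.0% (5.7 to 51.0) | 2/12 = 16.7% (4.7 to 44.8) | 4/12 = 33.3% (13.8 to 60.9) |

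The gap between the Synopsis and all-injected columns is 25.0 − 18.2 = 6.8 points for k = 1 and 33.3 − 20.0 = 13.3 points for k = 2.

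**Step 5. Chance of at least one such case.** With an assumed probability w per subject of an index AKA or death in the wait, it is 1 − (1 − w)^12: 46% for w = 5%, 72% for w = 10% and 93% for w = 20%.

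**The case against.** The BKA wording may only separate BKA from AKA candidates. Table 3 admits any major lower-extremity amputation, conversion is defined only after a BKA, and stump complications need a stump. That is a fair account of the purpose, but read literally the sentence still selects on the operation performed.

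The plan also limits the risk in the wait. Amputation must be safely deferrable, ulceration or gangrene must lie distal to the malleoli, earlier amputation is possible, and section 7.3.2 suspends enrollment for related or possibly related Grade 3 or worse infection, bleeding or tissue reaction at the index site. These provisions make such cases less likely but do not say how to count them.

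Several stronger inferences are tempting, and the documents do not support them:
- *All efficacy is restricted to BKA.* Only the Synopsis says so.
- *Death in the wait is excluded.* It lies outside the Synopsis comparison, but death is a named component in section 9.3, so its status there is open.
- *The protocol expects progression in that week.* Section 6.1.2 is conditional, and its sentence on evolving infection is not tied to the wait.
- *Historical follow-up starts at amputation, so bias in favor of BMAC is shown.* No section defines historical time zero. The direction is plausible, not demonstrated.
- *Rates of 25% or 33% can be set against 19%.* The 19% is an upper background figure for conversion after BKA. The all-injected rates also count index AKAs, so the two are not like for like. Every interval shown above contains 19%.

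**Conclusion.** The concern holds in limited form. The Synopsis conditions its comparison on a status fixed after injection, and the other sections differ from it on population. None supplies a time origin, denominator or counting rule for the interval before amputation. Followed as written, the plan never counts an index AKA in a subject planned for BKA as a failure.

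This can flatter the exploratory trend. Its size cannot be estimated from the documents: the 7 and 13 point gaps rest on assumed counts of one and two index AKAs, two later conversions, and all 12 subjects being BKA candidates. The intervals are far wider than those gaps, so the issue is how a trend is described, not a test result. Because efficacy is exploratory and unpowered, priority is moderate.

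**What to change.** - Reconcile the Synopsis with sections 3, 7.1 and 9.3 on who is in the efficacy analysis.
- In section 9.3, report efficacy in all injected subjects, grouped by the amputation level planned on injection day and timed from injection. Count death before amputation, or an index amputation above the planned level, as an event. State how earlier amputation is handled, and whether gangrene seen before surgery counts, given that Table 3 allows distal gangrene at entry.
- Beside it, report the BKA-only result timed from amputation for the comparison with historical controls. Use the injection-origin result against them only where historical time zero and planned level can be aligned, for example from the decision to amputate. Starting only the BMAC clock at injection would create the opposite mismatch.
- In Table 4, add two items at Visit 3: level planned against level performed, and the infection and gangrene check.

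The cost is protocol wording and two case report form fields at an existing visit. Treatment and visit timing do not change. The reported rate may look less favorable, and the all-injected result may have no exact historical counterpart.

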## Abbreviations

ABMNC	Autologous Bone Marrow Mononuclear Cells
ACS	Acute coronary syndrome
AE	Adverse event
AKA	Above Knee Amputation
ATM	Anterior tibialis muscle
BKA	Below Knee Amputation
BMAC	Concentrated bone marrow aspirate
cGCP	Good Clinical Practice
cGLP	Good Laboratory Practice
CHAMP	C linical and H istological A nalysis of concentrated autologous concentrated bone M arrow aspirate (BMAC) in amputations (MarrowCHAMP)
CLI	Critical Limb Ischemia
CTSI	Clinical and Translational Sciences Institute
DMSB	Data Monitoring and Safety Board
HIF-1 $\alpha$	Hypoxia Inducible Factor-1 $\alpha$
ICA	Indocyanine angiography
ICF	Informed consent form
ICH	International Conference on Harmonization
IHC	Immunohistochemical staining
IM	Intramuscular
LEADs	Lower Extremity Arterial Dopplers
LC-MS	Liquid Chromatography- Mass Spectrometry
MHC	Major Histocompatibility Complex
MSC	Mesenchymal Stromal Cell
PAD	Peripheral Arterial Disease
PCR	polymerase chain reaction
PHC	Proangiogenic Hematopoietic Cell
PI	Principal Investigator
SAE	Serious adverse event
SDF-1	Stromal Cell Derived Factor-1
TcPO 2	Transcutaneous oxygen pressure

## 1 INTRODUCTION

Critical limb ischemia (CLI) is the endstage of atherosclerotic peripheral arterial disease (PAD) and occurs when there is insufficient blood flow to meet the resting metabolic demands of the leg. The clinical features of CLI are rest pain and gangrene, both heralding signs of limb loss. Despite advances in surgical and endovascular revascularization techniques, approximately 40% of patients with CLI will require amputation of the affected extremity within one year. Most surgeons approach amputation in neurologically intact patients with the goal to save as much limb length as possible to promote independent ambulation with a limb prosthesis. Consequently, below knee amputation (BKA) is the most common amputation procedure performed in the U.S. However, contemporary studies and review of our own series demonstrate conversion rates from a BKA to AKA as high as 19% with the primary cause being ischemic wound complications of the myocutaneous flaps below the knee. The physiological consequences of loss of the knee joint with AKA, as compared to BKA, is a 40-60% increase in energy expenditure in ambulation with a prosthesis. This excessive effort results in a decreased rate of independent ambulation after AKA as compared to BKA (< 33% vs. > 65%, respectively) and translates into decreased quality of life, increased institutionalization, and increased health care costs for AKA patients. Thus, a procedure that may improve perfusion and promote wound healing of a lower extremity amputation stump may provide significant benefits to this patient population.

Bone marrow derived progenitor cells have been shown to respond to crosstalk with injured cells to limit tissue destruction or enhance repair by a variety of mechanisms that include (a) secretion of bioactive proteins that act in a paracrine or autocrine fashion; (b) upregulation of genes that modulate excessive inflammatory and immune reactions; and (c) transfer of vesicular components that contain mitochondria and microRNAs. For example, evidence supports the hypothesis that the predominant mechanisms driving tissue repair in a heart post-infarction is angiogenesis orchestrated via the release of stem-cell derived paracrine factors. Cumulative data regarding the bioactivity of bone marrow cells has been derived entirely from animal models of disease despite the fact that more than 120 clinical trials listed in *clinicaltrials.gov* use bone marrow derived cells for therapeutic endpoints. Furthermore, the translation of these data to human conditions is limited by the genomic discordance between mouse and human responses in pathological conditions. Seoka and colleagues found that among genes that changed significantly in humans in response to inflammatory stresses, the murine orthologs were close to random in matching their human counterparts. To date, no clinical trials have been designed with the ability to harvest human tissue post-cell implantation at time points relevant to their tissue reparative activity and survival. Thus the *in vivo* biological activity and survival of transplanted bone marrow derived cells in diseased human tissue remains undefined.

The BioCue™ Blood and Bone Marrow Aspirate (BMAC) Concentration System is used to process blood and bone marrow aspirate to produce an autologous PRP output for use in autograft and/or allograft therapies. The BioCue™ device is the exact same device as the MarrowStim™ PAD Kit that was used to treat subjects in prior versions of this protocol. Treatment includes removal of approximately 300 mL of bone marrow from the patient's posterior or anterior iliac crest, which is then mixed with an anticoagulant solution and processed in the BioCue™ device to concentrate the autologous bone marrow cell suspension for delivery. The subsequent treatment utilizes this BMAC at the point of care by injection to multiple sites in the affected leg. The BioCue™ BMAC product is hypothesized to function via angiogenic mechanisms. To date there are no comprehensive descriptive analyses of the fate of BioCue™ BMAC cells after transplantation in human tissue. Thus we propose a pilot trial, **Safety and Efficacy of Concentrated Autologous Concentrated Bone Marrow Aspirate (BMAC) in Preventing Wound Complications in Amputations (The MarrowCHAMP Study)**, that will help discern the mechanisms of therapeutic action in man. MarrowCHAMP will address two critical areas simultaneously:

assessing the efficacy of BMAC in preventing wound complications in lower extremity amputations and providing tissue at BioCue™ injections sites from a controlled time-point for first in man biochemical and histological analyses.

